## 6 STUDY TREATMENT

### 6.1 Study Treatment(s) Administered

#### 6.1.1 Investigational Products

**Table 13** Investigational Products

Treatment	RXC004	Nivolumab	Denosumab
ARM	Arm A and B	Arm B and Arm A combination treatment phase	Arm A and B
Type	Drug	Biologic	Biologic
Dose Formulation	0.5 mg or 1 mg capsules	Ampule	Ampule
Dosage Level(s)	Monotherapy: 2 mg QD Combination therapy: 1.5 mg QD	480 mg q4w	120 mg once every month
Route of Administration	oral	IV infusion	SC injection
Use	Experimental	Experimental	Prophylactic
IMP and NIMP	IMP	IMP	IMP
Sourcing	Provided centrally by the Sponsor	Provided centrally by the Sponsor	Provided centrally by the Sponsor
Packaging and Labelling	RXC004 will be provided in white 50 mL HDPE Duma bottles. Each bottle will be labelled as required per country requirement	Study Intervention will be provided in packets of 240 mg/24 mL vials. Each packet will be labelled as required per country requirement	Study Intervention will be provided in a vial containing 120 mg in 1.7 mL solution  Each vial will be labelled as required per country requirement

HDPE, high-density polyethylene; IMP, investigational medicinal product; IV, intravenous; NIMP, non-investigational medicinal product; QD, once daily; q4w, once every 4 weeks; SC, subcutaneous.

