Any event that meets nivolumab treatment hold (see Appendix G)	Interrupt nivolumab and manage as per Appendix G. Nivolumab can be re-started when event is resolved to ≤Grade 1 and any steroid taper completed (to ≤10 mg prednisone equivalent). RXC004 can continue whilst nivolumab is held if the patient is judged (by the investigator) to be receiving clinical benefit.
Grade 3 toxicity (1 st event)	RXC004 related; Interrupt RXC004 and provide supportive care, resume at a lower dose level when resolved (grade ≤ 2 or returns to baseline). See Table 15 for dose reduction scheme.
	Nivolumab related; See guidelines in Appendix G.
Grade 3 toxicity (subsequent recurrence of a previously experienced event)	RXC004 and/or nivolumab related; Permanently discontinue the related study treatment.

Event	Action
Grade 4 toxicity	RXC004 and/or nivolumab related; Permanently discontinue RXC004 and nivolumab (if applicable)
All Grade events	Study treatment can be interrupted or discontinued for any clinically significant AEs that in the investigator's opinion warrants treatment interrupted or discontinuation.
Bone events	
Confirmed (by imaging) RXC004 related fragility bone fracture (excluding grade 1 vertebral deformities)	Permanently discontinue RXC004. Nivolumab can continue if the patient is receiving clinical benefit as judged by the investigator.
Patients with a DXA scan showing $\geq 7\%$ worsening in BMD at lumbar spine or total hip compared to baseline	Permanently discontinue RXC004. Nivolumab can continue if the patient is receiving clinical benefit as judged by the investigator.
An individual increase in $\beta$ -CTX of CCI pg/ml from the baseline (screening) value or an individual measurement of CCI pg/ml	Permanently discontinue study treatment unless the patient has received clinical benefit (investigator assessment) and continued treatment is warranted.
COVID-19 infection	
Positive COVID-19 test	Interrupt RXC004, until acute symptoms have resolved.
Major surgery	
	Interrupt RXC004, resume at full dose. Nivolumab does not need to be interrupted.
	No stoppage is required for biopsy procedures.
Vomiting	
	If vomiting occurs shortly after RXC004 is swallowed, the dose may be replaced if all of the intact capsules can be counted. Resume with the following scheduled dose.
Missed RXC004 dose	

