	Allowed to take the scheduled dose up to 4 hours after the scheduled dose time. If greater than 4 hours, the missed dose should not be taken, and patient should continue with next dose at allotted time.

a Attempts should be made to confirm that the colitis has resolved to Grade  $\leq 1$  (e.g. normalised CRP or fecal calprotectin if raised during event; GI appearance normalised on X-ray/CT or endoscopy) before restarting RXC004.

AE, adverse event; BMD, bone mineral density; COVID-19, Coronavirus disease 2019; QD, once daily.

Toxicity will be assessed utilizing the NCI Common Terminology Criteria for Adverse Event (CTCAE) version 5.0, unless otherwise specified. Every effort should be made to administer trial treatment at the planned dose and schedule. However, patients experiencing RXC004 related toxicities may have their RXC004 dose modified as outlined below.

RXC004 related toxicities observed during the course of the study will be managed by interruption of RXC004 and initiation of appropriate treatment as judged by the Investigator. Upon re-starting treatment the guidance for dose reduction in RXC004 contained in Table 15 should be followed.

Patients in Arm A who have undergone dose reduction during monotherapy cannot have the RXC004 dose re-escalated if switching to RXC004 + nivolumab combination therapy. The RXC004 dose must be discussed with the Sponsor prior to starting combination therapy.

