**Table 15 Guidance for dose reductions for RXC004-related adverse events**

Dose Level	RXC004 (monotherapy)	RXC004 (in combination therapy)
Initial dose level	2 mg QD	1.5 mg QD
1 st dose reduction	
 
Grade 3 toxicity (1st event)
 
Grade 2 dysgeusia associated with 10-20% weight lossa
 
 
Hold RXC004b. Upon resolution to ≤ grade 2, restart at 1.5 mg QD
 
Dose reduce to 1.5 mg QD
	
Hold RXC004b. Upon resolution to ≤ Grade 2, restart at 1.0 mg QD
 
Dose reduce to 1.0 mg QD

2 nd dose reduction	
 
Grade 3 toxicity (1st unique event)
 
Grade 3 toxicity (recurrence of a previously experienced Grade 3-4 event)
 
Grade 2 dysgeusia associated with >20%
 
 
Hold RXC004b. Upon resolution to ≤ grade 2, restart at 1 mg QD
 
Permanently discontinue RXC004
 
Permanently discontinue RXC004
	
Hold RXC004b. Upon resolution to ≤ Grade 2, restart at 0.5 mg QD
 
Permanently discontinue RXC004
 
Permanently discontinue RXC004

Dose Level	RXC004 (monotherapy)	RXC004 (in combination therapy)
weight loss a		
3 rd dose reduction	Not permitted. Permanently discontinue RXC004	Not permitted. Permanently discontinue RXC004

a excluding other possible causes and despite optimal treatment  
 b RXC004 can be resumed after an interruption, as long as no other treatment discontinuation criteria have been met. Patients who experience disease progression whilst RXC004 is held, will not be eligible to be treated beyond progression.

For patients treated with RXC004 and nivolumab, dose reductions in nivolumab are not allowed. Patients experiencing nivolumab related toxicities may delay nivolumab infusions or permanently discontinue nivolumab as described in Appendix G and Table 14.

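### The major-surgery row of Table 14 restarts RXC004 at an undefined full dose, with no exception for patients already reduced for toxicity, and so does not fit Table 15 or the overdose definition

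*Protocol*

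**What the plan says.** The major-surgery row of Table 14 reads "Interrupt RXC004, resume at full dose. Nivolumab does not need to be interrupted". It applies to every patient, does not refer to Table 15, and is silent on earlier reductions.

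The surrounding text is as follows.

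- **Starting levels.** Table 13 gives "Monotherapy: 2 mg QD Combination therapy: 1.5 mg QD". Table 15 labels the same two doses as the initial level.
- **Table 15.** Its title is "Guidance for dose reductions for RXC004-related adverse events". For a first reduction it says "Dose reduce to 1.5 mg QD" on monotherapy and "Dose reduce to 1.0 mg QD" on combination. The second step on monotherapy is "restart at 1 mg QD"; on combination it is 0.5 mg QD. A third reduction is not allowed and means permanent discontinuation. The table has no upward step.
- **Toxicity rows of Table 14.** After colitis of Grade 2 (either regimen) or Grade 3 (monotherapy), or after a first related Grade 3 toxicity, RXC004 resumes at a lower level, with a pointer to Table 15.
- **Re-escalation.** Section 6.6, between the two tables, says that Arm A patients reduced on monotherapy "cannot have the RXC004 dose re-escalated if switching to RXC004 + nivolumab combination therapy". Section 4.1 and the note to Figure 1 repeat this.
- **Overdose.** Section 8.4 counts any RXC004 dose above the patient's assigned daily dose as an overdose.

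**The concern.** A patient reduced for related Grade 3 toxicity, colitis, or dysgeusia with weight loss may later need an operation. The only instruction for restarting after surgery names a full dose. Two sites could act on it differently in good faith: one restarts at the initial level, the other at the level the patient was on before surgery. On the first reading the patient goes back to the dose at which the toxicity arose, shortly after major surgery.

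This also bears on whether treatment continues. Table 14 requires permanent discontinuation of the related drug when a previous Grade 3 toxicity recurs at Grade 3. Appendix J requires it when colitis of Grade 2 or higher recurs after restart. The protocol also does not say whether reductions made before surgery still count towards the Table 15 limit once a patient is back at the initial level.

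**Working it through.** The plan states no figure on this point, so the check sets the passages side by side and then sizes the literal reading.

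**1. What full dose can mean.**

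| Reading | Supporting text | Result for a reduced patient |
|---|---|---|
| Initial level (2 mg or 1.5 mg) | Ordinary meaning; contrast with the lower-dose wording of the toxicity rows; Section 6.6 urges sites to keep to the planned dose; SAP Section 4.10.1 computes relative dose intensity against 2 mg or 1.5 mg whatever reductions occurred | Dose goes up |
| Level held before surgery | Section 6.6 opens by permitting reduction and interruption, without mention of re-escalation; Section 8.4 refers to an assigned daily dose; SAP Section 4.10.1 tabulates reductions (any, 1, 2) and has no category for increases | No change |

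No sentence decides between the two.

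**2. Size of the dose change under the literal reading.** Ratio = initial dose / reduced dose, with doses from Tables 13 and 15.

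- Monotherapy, after one reduction: 2 / 1.5 = 1.33.
- Monotherapy, after two reductions: 2 / 1 = 2.
- Combination, after one reduction: 1.5 / 1.0 = 1.5.
- Combination, after two reductions: 1.5 / 0.5 = 3.

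Under the other reading every ratio is 1.

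**3. Exposure, as an indication only.** Ratios of the steady-state geometric means in Table 12 (Phase 1):

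| Change | Parameter | Ratio | n (CV), lower dose | n (CV), higher dose |
|---|---|---|---|---|
| Monotherapy 1 to 2 mg | AUC0-24 | 931 / 392 = 2.4 | 3 (42%) | 4 (61.1%) |
| Monotherapy 1.5 to 2 mg | AUC0-24 | 931 / 630 = 1.5 | 6 (76%) | 4 (61.1%) |
| Combination 1.0 to 1.5 mg | AUC0-24 | 706 / 544 = 1.3 | 5 (65.5%) | 5 (40.1%) |
| Monotherapy 1 to 2 mg | Cmin | 26.8 / 7.15 = 3.7 | 3 (120%) | 4 (134%) |

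These compare separate small cohorts, not the same patients at two doses. Section 4.4.1.3 describes exposure from 0.5 to 2 mg as broadly dose proportional, so the dose ratios in step 2 are the safer guide.

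**4. Which rule is engaged for which patient.**

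- *Arm B, and Arm A patients staying on monotherapy.* The re-escalation sentence does not reach them. Table 15 covers RXC004-related adverse events, not surgery, and does not call a reduction permanent. What remains is a ladder that only goes down, an overdose definition tied to the assigned dose, and a surgery row that fits neither if read literally.
- *Arm A switchers who entered combination below 1.5 mg.* The re-escalation sentence kept them below the initial combination dose. A literal restart at 1.5 mg removes that protection, although the sentence itself speaks of the switch and not of a later surgical hold.

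**The case against.** The strongest reply is that the row means only that surgery is not in itself a reason to reduce. Beside rows telling sites to resume at a lower dose, full dose may simply say that no step down is needed. The opening of Section 6.6, the overdose definition and the SAP's exposure tables all sit comfortably with this. It is a reasonable reading and may be the intended one. But none of these passages defines the term, and the literal reading has support in the same section.

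A reader might infer that the row directly contradicts a protocol-wide ban on re-escalation, or Table 15 itself. The documents do not support that. The ban is confined to Arm A patients at the switch to combination. The sentence sending restarts to Table 15 follows one about RXC004-related toxicity, so it does not govern surgical holds.

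A reader might also take 9 of 25 in Phase 1 Table 5 as the share of patients at risk. That row counts dose modification of any kind and includes 2 patients at 3 mg and 1 at 10 mg, neither of which is a dose in this study. In the combination module (Table 9), where the two are separated, 7 of 13 had a modification but only 1 of 13 a reduction. The figure is not a usable proxy.

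Finally, discontinuation on recurrence applies at any dose level, so this row does not create that rule. That is correct. The row matters only because, on one reading, it puts the patient back at the level where the toxicity first occurred.

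**Conclusion.** The point stands in limited form. The major-surgery row is an unqualified restart instruction built on an undefined term. It has two materially different readings for a patient already reduced. The literal one raises the daily dose 1.33- to 2-fold on monotherapy and 1.5- to 3-fold on combination. It fits neither the downward-only scheme of Table 15 nor the overdose definition in Section 8.4, and it undoes the protection given to Arm A patients who switched below 1.5 mg. For all other patients it is an inconsistency with evident intent, not a breach of a stated rule.

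The dose ratios assume that full dose means the initial level; if it means the level held before surgery, there is no increase. Few patients can be affected: they must have been reduced, then have major surgery, then resume, in a study planned around 20 evaluable patients per arm. Their number is not given, and no material effect on DCR, ORR or the dose-intensity summaries has been shown. The case for correction rests on individual patient safety and uniform conduct across sites, and on how little the correction costs.

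**What to change.** Reconcile the major-surgery row of Table 14 with Table 15, the no-re-escalation sentence in Section 6.6 and the overdose definition in Section 8.4. The text should state one restart level for a patient already reduced, separately for monotherapy and combination, and cover Arm A switchers explicitly. It should also say whether earlier reductions still count towards the Table 15 limit after a surgical restart. Which level applies is for the sponsor to decide; this review takes no view.

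If the sponsor's answer allows a dose increase after surgery, the SAP exposure section (4.10.1) should gain a category for it, since only reductions and interruptions are counted now.

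The cost is about one sentence in Table 14 at the next amendment and a memo to sites meanwhile. Sample size and data collection are unaffected.

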**Table 15 Guidance for dose reductions for RXC004-related adverse events**

Dose Level	RXC004 (monotherapy)	RXC004 (in combination therapy)
Initial dose level	2 mg QD	1.5 mg QD
1 st dose reduction	
 
Grade 3 toxicity (1st event)
 
Grade 2 dysgeusia associated with 10-20% weight lossa
 
 
Hold RXC004b. Upon resolution to ≤ grade 2, restart at 1.5 mg QD
 
Dose reduce to 1.5 mg QD
	
Hold RXC004b. Upon resolution to ≤ Grade 2, restart at 1.0 mg QD
 
Dose reduce to 1.0 mg QD

2 nd dose reduction	
 
Grade 3 toxicity (1st unique event)
 
Grade 3 toxicity (recurrence of a previously experienced Grade 3-4 event)
 
Grade 2 dysgeusia associated with >20%
 
 
Hold RXC004b. Upon resolution to ≤ grade 2, restart at 1 mg QD
 
Permanently discontinue RXC004
 
Permanently discontinue RXC004
	
Hold RXC004b. Upon resolution to ≤ Grade 2, restart at 0.5 mg QD
 
Permanently discontinue RXC004
 
Permanently discontinue RXC004

Dose Level	RXC004 (monotherapy)	RXC004 (in combination therapy)
weight loss a		
3 rd dose reduction	Not permitted. Permanently discontinue RXC004	Not permitted. Permanently discontinue RXC004

a excluding other possible causes and despite optimal treatment  
 b RXC004 can be resumed after an interruption, as long as no other treatment discontinuation criteria have been met. Patients who experience disease progression whilst RXC004 is held, will not be eligible to be treated beyond progression.

For patients treated with RXC004 and nivolumab, dose reductions in nivolumab are not allowed. Patients experiencing nivolumab related toxicities may delay nivolumab infusions or permanently discontinue nivolumab as described in Appendix G and Table 14.

## 6.7 Access to Study Treatment after the End of the Study

Any patients still receiving investigational product at the time of the data cut off will be able to continue to receive investigational products within the current study, if in the Investigator's opinion, they are deriving clinical benefits and not meeting any of the discontinuation criteria. Assessments will revert to standard of care for each individual site. Patients will continue to be monitored for all SAEs up to 30 days after the last dose of RXC004 (for patients treated with RXC004 monotherapy only) or 90 days after the last dose of nivolumab (for patients treated with RXC004 and nivolumab). A paper form process will be used for SAE reporting.

All SAEs, overdoses and pregnancies will be reported until 30 days after the last dose of RXC004 (for patients treated with RXC004 monotherapy only) or 90 days after the last dose of nivolumab (for patients treated with RXC004 and nivolumab). The investigational product will be supplied to sites manually. The investigational product dispensation and reconciliation will be handled by the study at each patient's visit. The investigational product accountability information must still be collected until all patients have completed treatment.

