\*\*~~CCI~~ [REDACTED], ideally from the same site of disease (e.g. liver, lymph node etc) that the 'on treatment' biopsy will be taken from, and taken after completion of all prior standard of care treatments will be accepted as a baseline biopsy.

- 8 Patients with adequate organ functions as described below;
  - AST/ALT  $\leq$  2.5X ULN (upper limit of normal) [with no underlying Liver Metastasis]
  - AST/ALT  $\leq$  5 X ULN [with underlying Liver Metastasis]
  - Total Bilirubin  $\leq$  1.5 X ULN
  - Serum Creatinine  $\leq$  1.5 X ULN
  - ANC  $\geq$  1.5  $\times$  10^9/L
  - Platelets  $>$  100  $\times$  10^9/L
  - Hb  $>$  8.5g/dL (with or without transfusional support)
  - Calculated creatinine clearance (CrCL)  $\geq$  60 mL/min as determined by Cockcroft Gault (using actual body weight).

Males:

$$\text{CrCL} = \frac{\text{Weight (kg)} \times (140 - \text{Age})}{72 \times \text{serum creatinine (mg/dL)}}$$

Females:

$$\text{CrCL} = \frac{\text{Weight (kg)} \times (140 - \text{Age})}{72 \times \text{serum creatinine (mg/dL)}} \times 0.85$$

- 9 Female patients of childbearing potential must have a negative pregnancy test prior to start of dosing
- 10 Female patients of childbearing potential and male patients with female partners of childbearing potential must agree to use a highly effective method of contraception during the study and for at least 5 months after the last dose of study drug. See Section 5.3.1 for details of acceptable methods of contraception

**For patients on RXC004 monotherapy treatment (Arm A) the following inclusion criteria will also apply to enter the RXC004 + nivolumab treatment phase;**

11. Patients must have had documented RECIST1.1 defined radiological progression on RXC004 monotherapy treatment on the first scheduled scan (week 8 +/- 1 week)
12. Patients must receive Cycle 1 Day 1 of combination study treatment within 28 days of the first scheduled scan (week 8 +/- 1 week) showing RECIST1.1 defined radiological progression, or for clinically stable patients that remain on RXC004 after RECIST1.1 defined radiological progression, within 28 days of the most recent scan showing further radiological progression or confirmation of the week 8 RECIST1.1 progression (see Section 7.1.1 and Appendix D for more details)

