### **5.3 Lifestyle Considerations**

#### **5.3.1 Contraception**

- 1 Women must be 1 year post-menopausal, surgically sterile or must agree to using enhanced contraceptive measures for the duration of the study and for 5 months after the last dose of study drug, with all male sexual partners. Highly effective methods of contraception must be used, which include having a vasectomised partner, sexual abstinence (defined as refraining from heterosexual intercourse during the study and for 5 months after the last dose of study drug. The reliability of sexual abstinence needs to be evaluated by the Investigator, in relation to the duration of the study and the preferred/usual lifestyle of the subject), or one of the following: hormonal contraceptives which inhibit ovulation (oral, injectable, transdermal, intravaginal or implants), Intrauterine Device (IUD), Intrauterine Hormone-releasing System (IUS) (e.g., Mirena), or bilateral tubal occlusion.
- 2 Men must use a condom (with spermicide) during the study, and for 5 months after the last dose of study drug, with all sexual partners.
- 3 Men must not donate sperm for 5 months after the last dose of study drug.

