### 8.3.10 Pregnancy

All pregnancies and outcomes of pregnancy should be reported to Sponsor representative except for if the pregnancy is discovered before the study participant has received any study

drug.

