### **8.3.10.1 Maternal Exposure**

The Sponsor and Sponsor designated Safety Services must be notified **within 24 hours** of the initial report and any follow-up reports of a female patient or a male patient's female partner becoming pregnant during the course of the study and for 5 months after the last dose of the study drug(s) via the Pregnancy Report Form. Pregnancy itself is not regarded as an adverse event unless there is a suspicion that the investigational product under study may have interfered with the effectiveness of a contraceptive medication or a female patient or male patient's female partner experiences signs or symptoms of pregnancy complications; congenital abnormalities/birth defects and spontaneous miscarriages should be reported as SAEs. The contact information for pregnancy reporting is the same as for SAE reporting. Female patient(s) who become pregnant will be followed until the outcome of the pregnancy is known. In order for the Sponsor or designee to collect pregnancy surveillance information, the pregnant patient or partner must sign an ICF. Pregnancy follow-up should describe the outcome of the pregnancy, including any voluntary or spontaneous termination, details of the birth, and the presence or absence of any congenital abnormalities or birth defects in the offspring.

If a female patient becomes pregnant, administration of the study drug(s) must be discontinued immediately.

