### **8.3.10.2 Paternal Exposure**

Male participants should refrain from fathering a child or donating sperm during the study and for at least 5 months following the last dose.

Pregnancy of the participant's partners is not considered to be an adverse event. However, the outcome of all pregnancies (spontaneous miscarriage, elective termination, ectopic pregnancy, normal birth or congenital abnormality), occurring from the date of the first dose until 5 months after the last dose should, if possible, be followed up and documented in the Pregnancy Report Form. Consent from the partner must be obtained before the Pregnancy Report Form is completed.

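### For patients still dosing after data cut-off, Protocol Section 6.7 stops pregnancy reporting at 30 or 90 days, against 5 months in Section 8.3.10.1 (minor safety-reporting inconsistency)

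*Protocol*

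**What the plan says.** Protocol Section 6.7 covers patients still receiving investigational product at data cut-off. They may continue within the current study if they are benefiting and meet no discontinuation criterion. For monotherapy patients the section states: "All SAEs, overdoses and pregnancies will be reported until 30 days after the last dose of RXC004". For patients who have had both drugs, the same sentence sets the limit at 90 days after the last nivolumab dose.

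Section 8.3.10 has its own rule for pregnancy: "All pregnancies and outcomes of pregnancy should be reported to Sponsor representative". Its one exception is a pregnancy discovered before any study drug was taken. Section 8.3.10.1 requires notification within 24 hours of a patient or a male patient's partner "becoming pregnant during the course of the study and for 5 months after the last dose of the study drug(s". Section 8.3.10.2 asks that the outcomes of partner pregnancies "occurring from the date of the first dose until 5 months after the last dose" be followed up and documented, if possible and with the partner's consent.

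Contraception runs for the same period in both arms. Under Section 5.1, criterion 10, patients must "agree to use a highly effective method of contraception during the study and for at least 5 months after the last dose". Under Section 5.3.1, women who are neither post-menopausal nor sterile must "agree to using enhanced contraceptive measures for the duration of the study and for 5 months after the last dose of study drug". Section 5.3.1 also sets 5 months for men.

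**The concern.** The same event, in the same patient, has two reporting deadlines. The 30- and 90-day limits in Section 6.7 are those used for adverse events and SAEs in Section 8.3.1. It looks as though pregnancy was swept into a sentence written for SAEs. No reason is given for a shorter pregnancy window after cut-off, and the contraception duty is not shortened to match.

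At stake is the prospective reporting of uncomplicated pregnancies. Take a monotherapy patient who becomes pregnant 60 days after the last RXC004 dose. Section 8.3.10.1 requires notice within 24 hours and follow-up to outcome. A site working from Section 6.7, the section written for this situation, would find the window already closed. Follow-up to outcome begins with the pregnancy report, so a missed report can mean a missed outcome.

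**Working it through.** The plan gives no figure to reproduce. The check compares text and converts months to days.

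**Inputs**
- Section 6.7, monotherapy: 30 days after the last RXC004 dose.
- Section 6.7, combination: 90 days after the last nivolumab dose.
- Section 8.3.10.1: 5 months after the last dose of study drug(s).
- Month length: 30.4375 days. SAP Section 4.11.3.2 uses this for PFS rates; it is borrowed here only to express months in days.
- Protocol Table 14: after nivolumab is permanently discontinued, RXC004 may continue if the investigator judges that there is clinical benefit.

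**Step 1. The longer window in days.** 5 × 30.4375 = 152.2 days.

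**Step 2. Days not covered by Section 6.7, read literally**

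| Situation | Section 6.7 window | Uncovered days | Share of 152.2 days |
|---|---|---|---|
| Monotherapy | 30 days | 152.2 − 30 = 122.2 | 80% |
| Combination, both drugs stopped together | 90 days | 152.2 − 90 = 62.2 | 41% |

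**Step 3. Combination, nivolumab stopped first.** Let d be the number of days RXC004 continues after the last nivolumab dose. Counted from the last RXC004 dose, the Section 6.7 window ends at 90 − d days, so the gap is 152.2 − (90 − d) = 62.2 + d days. If d exceeds 90, the window closes before RXC004 is stopped. Table 14 permits this sequence; the documents do not say how often it is expected.

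**Step 4. Does either section yield to the other?** Section 8.3.10 has no exception for the period after cut-off. Section 6.7 does not refer to Section 8.3.10 and does not say that it replaces it. The patients concerned remain in the current study, so Section 8.3.10 still applies to them on its face. The conflict is in the current text and is not resolved there.

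**The case against.** The strongest reply is that the stricter rule is still in force. Section 6.7 does not say that pregnancies are reported only up to its limits, and nothing disapplies Section 8.3.10. A site that reports for 5 months satisfies both sections. This is correct. A reader might infer that the protocol switches off 5-month reporting after cut-off, or permits sites to stop early; the documents do not support that. What remains is that the section addressed to these patients states a shorter period and gives no pointer to the longer one.

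A reader might also infer that serious pregnancy outcomes would be lost. That goes too far. Section 8.3.10.1 says that "congenital abnormalities/birth defects and spontaneous miscarriages should be reported as SAEs", and Section 8.3.1 requires an investigator who becomes aware of a suspected-related SAE after the end of the study to report it. The backstop is partial: the SAE window in Section 6.7 is equally short, and the late route depends on awareness and suspected causality. It does exist, however.

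Two further objections stand. Section 8.3.10.2 is a best-efforts clause for partner follow-up, so the firm 5-month requirement rests on Section 8.3.10.1. And the 80% and 41% are shares of a calendar window. They do not measure risk: the number of patients dosing after cut-off is not given, about 20 evaluable patients are planned per arm, and pregnancies in the gap may well be close to none.

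Finally, because Section 6.7 also says "Assessments will revert to standard of care for each individual site", a reader might see a parallel defect in bone monitoring, since the DXA stopping rule in Table 14 is retained. The documents do not support treating that as an inconsistency. The section declares the change openly, DXA is not forbidden, and mandating scans would be a new procedure and a matter of preference. A case for DXA on this ground would also have to deal with the beta-CTX stopping rule in the same block of Table 14.

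**Conclusion.** Section 6.7 is wrong as written on one item. For patients still dosing after data cut-off, its pregnancy reporting period conflicts with Section 8.3.10.1 and falls short of the contraception period. Read literally, the shortfall is about 122 days for monotherapy and about 62 days for combination with both drugs stopped together. It grows by one day for each day RXC004 continues after nivolumab. These figures assume 30.4375 days per month and a site that applies Section 6.7 without reading Section 8.3.10.

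The inconsistency is minor. It is confined to patients treated past cut-off, who should be few, and the longer rule has not been withdrawn. It concerns safety reporting only and does not affect any endpoint, the sample size or the analysis. It is still worth correcting, because two deadlines for one safety report invite error and the correction is simple.

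**What to change.** In Protocol Section 6.7, remove pregnancies from the sentence on SAEs and overdoses and add: *Pregnancies will be reported until 5 months after the last dose of any study drug, as in Section 8.3.10.* Counting from the last dose of any study drug also stops the combination window closing while RXC004 continues.

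No change is proposed to DXA or beta-CTX after cut-off.

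The cost is one sentence. Under Appendix A 1 a protocol amendment needs ethics committee and regulatory approval, so the change is best carried in the next amendment. Until then, a short written reminder to sites that Section 8.3.10 applies to patients treated after cut-off would serve. Sites must keep the Pregnancy Report Form available for 5 months after the last dose, which Section 8.3.10 already requires. The change adds no visits, tests or patient obligations.
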